	dose level 1, then de-escalate to dose level 0. If this occurs at dose level 0, the trial will be terminated.				
$\leq 1$ out of 6 at highest dose level at or	This will be the RP2D.				
below the maximally administered					
dose					

#### **Table 9. Dose Escalation Schema**

## 13.2.4 Phase 2 Design

Once the RP2D has been identified, an additional 14 to 17 evaluable patients will be enrolled at the RP2D. Interim monitoring of treatment related mortality (TRM) of the 20 patients treated at the RP2D is described in section 13.5 below.

## 13.3 Sample Size, Accrual Rate and Study Duration

During Phase 1, a minimum of 3 evaluable patients will be required (if 0 out of 3 patients at dose level 1 experience a DLT, the RP2D has been identified). A maximum of 12 evaluable patients will be required (6 patients at dose level 1 followed by 6 patients at dose level 0).

During Phase 2, an additional 14 to 17 evaluable patients will be required to reach a total of 20 evaluable patients treated at the RP2D. A sample size of 20 evaluable patients achieves an exact 95% confidence interval width equal to 0.379 assuming that the observed proportion of patients experiencing a DLT is 0.20.

Total Sample Size. A minimum of 3 and a maximum of 26 evaluable patients will be required. To account for up to 2 potentially unevaluable patients, a maximum sample size of up to 28 patients is anticipated.

Study Duration. Assuming an accrual rate of 1 patient per month, accrual of the up to 28 patients will take about 2 years and 4 months, plus 2 years of follow-up on the last patient, for a total study duration of about 4 years 4 months.

## **13.4** Stratification Factors

There are no stratification factors in this trial.

#### 13.5 Interim Monitoring Plan

#### 13.51 Monitoring rule for TRM

A one-stage stopping rule will monitor transplant-related mortality (TRM) for the N=20 patients treated at the RP2D. TRM is defined as the occurrence of death from any cause from Day -7 pre-transplant to post-transplant Day +100.

The one-stage interim monitoring rule for TRM is presented in Table 10. If there are 3 or more transplant-related deaths in the 20 patients treated at the RP2D, enrollment to the trial will be suspended so that DSMC can consider terminating the trial. If there are 2 or fewer transplant-related deaths in the 20 patients treated at the RP2D, uproleselan will be declared as safe for further investigation in pediatric patients.

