# Treatment may not begin without confirmation from the coordinating center that the participant has been registered and enrolled on study.

# 5. TREATMENT PLAN

# 5.1 Treatment Regimen

This is a phase 1/2 trial comprised of a dose-finding phase (phase 1) to determine the RP2D of uproleselan followed by a dose expansion phase (phase 2) to further assess safety and to make a preliminary assessment of efficacy of the RP2D. In both phases, uproleselan will be combined with a high dose busulfan-based myeloablative conditioning regimen (busulfan, fludarabine, and clofarabine) starting with a single dose on day -8, followed by doses q12 hours (H) on conditioning day -7 and ending on day -2 (Table 1).

Table 1. Pre-transplant Conditioning				
Uproleselan with Busu	Uproleselan with Busulfan, Fludarabine, Clofarabine			
Days -8 to day -2	
 
Uproleselan will be administered IV over 20 minutes (+/- 2 minutes) per assigned dose level in the phase 1 portion or at the RP2D in the phase 2 portion. The maximum dose of uproleselan is 800mg BID. The 20 minute infusion time should include the line flush to ensure the full dose has been infused.
 
A single primer dose will be administered on day -8
 
Beginning on day -7 (with start of fludarabine, clofarabine and busulfan) 12 doses of uproleselan will be administered q 12 H.
 
The 1st, 3rd, 5th, and 7th of theses 12 doses (not including initial day -8 dose) should be administered sequentially, after clofarabine and just prior to busulfan. Delay of doses should be avoided.
 
The last dose of uproleselan will be administered 12 hours (+/- 60 minutes) after dose 11.
 
			
Days –7 to –4	Fludarabine 10 mg/m²/dose daily IV administered as a 30 minute*infusion immediately prior to clofarabineClofarabine 30 mg/m²/dose daily IV administered as a 120 minute*infusion immediately after fludarabine and just prior to uproleselanBusulfan IV daily IV over 3 hours administered immediately afteruproleselan.			
	See section 5.2.1 for details			

	• Busulfan exposure targeted to 80-100 mg x h/L		
Day -1	-1 Rest		
Day 0 Hematopoietic Stem Cell Infusion			
*Duration of infusion may be adjusted nor institutional standards			

\*Duration of infusion may be adjusted per institutional standards

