# Phase 2 Design

After completion of the phase 1 portion of the trial, enrollment at the recommended phase 2 dose will be expanded to bring total enrollment at this dose to 20 evaluable patients. Information about patients treated at the RP2D will be used to obtain preliminary estimates of drug exposure and efficacy, and to confirm safety. A one-stage stopping rule will monitor transplant-related mortality (TRM) for the 20 patients treated at the RP2D (see section 13.5).

Once the RP2D has been identified, an additional 14 to 17 evaluable patients will be enrolled at the RP2D. Interim monitoring of treatment related mortality (TRM) of the 20 patients treated at the RP2D (3 to 6 from Phase 1 and 14 to 17 from Phase 2) is described in section 13.5.

Treatment will be administered on an inpatient basis. Reported adverse events and potential risks are described in Section 7. Appropriate dose modifications are described in Section 6. No investigational or commercial agents or therapies other than those described below may be administered with the intent to treat the participant's malignancy.

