# 5.2 Agent Administration

Uproleselan will be administered as a 20 minute (+/- 2 minutes) IV infusion (including flush) with dose per assigned level. The maximum dose of uproleselan is 800mg BID. A single priming dose will be administered on Day -8. 12 additional doses will then be administered q 12 H beginning immediately after clofarabine and just before busulfan on Day -7. The dose of uproleselan can be rounded to the nearest whole unit to avoid decimal dosing. Dosing will be based on actual weight. Weight can be collected up to 7 days prior to first dose administration, if weight changes by >10% prior to first dose, dose will be adjusted to current weight. Doses of Uproleselan should not be adjusted once conditioning has started.

Reactions to uproleselan infusions have not been observed to date. Patients should have vital signs just prior to infusion and repeated with the start of the infusion three times at 10-minute (+/- 2 minutes) intervals. Frequent vitals can be discontinued if the patient has not manifested any signs of anaphylaxis or other serious infusion-related reaction. The infusion should be discontinued for any signs of anaphylaxis and the event should be reported immediately to the study team.

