# 7.5 Expedited Reporting

All SAEs must be reported to the Sponsor Investigator immediately, no later than 24 hours of first becoming aware of the event. All SAEs must be reported despite grade or whether or not considered drug related, including those listed in the protocol or investigator brochure and must include an assessment of whether there is a reasonable possibility that the drug caused the event.

The Sponsor Investigator ([name]) and DFCI study team

([contact]) should be informed by email within 24 hours of all SAEs that occur after the patient has provided informed consent, during treatment, or until the participant is taken off study. In the event that the participating investigator does not become aware of the SAE immediately, the participating investigator is to report the event within 24 hours of learning of it and document the time of his or her first awareness of the event.

The study site will have 5 business days from the discovery of the SAE to send a complete expedited report to the Sponsor Investigator.

In addition to SAEs, per DFCI's Expedited Reporting requirements, the following events also require expedited reporting unless they are specifically excluded in Section 7.3:

- Unexpected grade 2 or 3 with a possible, probable, or definite attribution
- Unexpected grade 4 toxicities regardless of attribution
- Dose limiting toxicities that are described in section 5.3

*Pregnancies*: To ensure patient safety, each pregnancy in a patient on study treatment must be reported to the Sponsor Investigator. Pregnancy follow-up should include an assessment of thepossible relationship to the study treatment any pregnancy outcome. Any SAE experienced during pregnancy must be reported. Additionally, pregnancy outcomes should be collected for the female partners of any male study participants. Consent to report information

regarding these pregnancy outcomes should be obtained from the pregnant partner. Sites should follow their institutional policies regarding consenting pregnant partners.

*Unanticipated problems or life-threatening complications:* In the event of an unanticipated problem or life-threatening complications that places subjects or other persons at greater risk of harm than previously recognized occurs, treating investigators must immediately notify the Sponsor-Investigator.

Sponsor-Investigator contact information:

- [name]
- Email: [name]
- [contact]
- DFCI lead study coordinator or study team: [contact]

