## 12.2 Data Safety Monitoring

This study will be centrally reviewed by the Data Safety and Monitoring Committee (DSMC) of the Pediatric Transplant and Cellular Therapy Consortium (PTCTC). This DSMC is chartered to monitor trials enrolling both children and adult patients. The DSMC is a standing committee, composed of a chair, patient advocate, biostatistician, nurse representative and 2 bone marrow transplant physicians with procedures and processes as defined in the PTCTC DSMC Charter. The DSMC will review the study protocol prior to study activation and IRB review, and will continue to review the study on a regular basis according to the committee rules. The DSMC will meet at regular intervals to review all adverse events and deaths and determine whether any patient safety problems necessitate protocol modifications or discontinuation of the trial. The DSMC will also meet on an ad hoc basis to review the results of interim analyses or if unexpected safety events occur that may necessitate study suspension or closure. The DSMC will discontinue the review of outcomes when administration of the study product has ended for all

subjects. The DSMC has the authority to unblind study personnel prior to study closure if, in their opinion, doing so will be critical to patient safety.

Before each regularly scheduled DSMC meeting, the study coordinator will submit a report including tabular summaries of all reported SAEs, AEs and deaths on study to date. The report will also include a brief summary of each previously unreported SAE and death, including an assessment of whether the event was unexpected or related to the study. If the DSMC recommends protocol or informed consent changes during the study, the recommendations will be reviewed by the Protocol Chair and incorporated into the protocol as deemed appropriate. The protocol with incorporated changes will be distributed to the participating PIs after approval by the Dana Farber Cancer Institute IRB. It is the responsibility of each Transplant Center PI to forward the distributed communications from the DSMC to their local IRB.

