## **13.1** Definition of Evaluability

13.1.1 Definition of Evaluability for Dose Escalation Evaluation (Phase 1)

Eligible patients who are evaluable for the dose-determining analysis are those who either: A) meet the following minimum exposure criterion and complete the DLT observation period without experiencing a DLT;

or

B) receive at least 1 dose of uproleselan and experience a DLT during the DLT observation period.

A patient is considered to have met the minimum exposure criterion if he/she received at least 10 of the 12 of planned doses of uproleselan in the first cycle of dosing. Patients who do not meet criteria for inclusion in the dose-determining analysis population will be replaced in the study accrual. 13.1.2 Definition of Evaluability for estimation of efficacy (Phase 2)

Eligible patients will be evaluable for estimation of efficacy if they have received at least one dose of uproleselan at the RP2D. Patients who do not receive any uproleselan will be replaced in the trial accrual.

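### The TRM window in 13.51 opens on Day -7, one day after the first uproleselan dose, so a death on Day -8 would not count in the 3-of-20 rule

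*Protocol*

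**What the plan says.** Section 5.1, Table 1, gives the start of study drug: "A single primer dose will be administered on day -8". Section 5.2 says the same, and Table 7 labels Day -8 as the first uproleselan dose for pharmacokinetic sampling. Fludarabine, clofarabine, busulfan and the twelve 12-hourly uproleselan doses begin on Day -7.

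Section 13.51 monitors mortality in the 20 patients treated at the RP2D and fixes the event by date of death: "TRM is defined as the occurrence of death from any cause from Day -7 pre-transplant to post-transplant Day +100". Three or more such deaths suspend enrolment so that the DSMC can consider termination. Two or fewer lead to a declaration that uproleselan is safe to investigate further in children (13.51 and Table 10). The rule is stated to have 92.5% power and 9.1% type 1 error, with a null death probability of 0.25 and an alternative of 0.05.

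**The concern.** The rule ends in a statement about uproleselan, yet its event window leaves out the day of first exposure. Day -8 is also the only day on which uproleselan is given before any of the conditioning chemotherapy. Section 2.1.3 notes that the trial is the first of this drug in children and the first in HSCT. Section 7.2 says that attribution is not judged for uproleselan alone, so an all-cause count is the natural formal check on mortality, and one would expect it to begin with the first dose.

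If a patient did die on Day -8, the count would not register it. The DSMC would then have to decide outside the written rule, after the event, how to treat that death.

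**Working it through.** **1. Compare the dates.**

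| Item | Start | Source |
|---|---|---|
| First uproleselan dose | Day -8 | Table 1; 5.2; Table 7 |
| Fludarabine, clofarabine, busulfan; 12-hourly uproleselan | Day -7 | Table 1 |
| TRM event window | Day -7 | 13.51 |

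No other section moves the TRM window back. Because the window goes by date of death, only a death on Day -8 itself is missed.

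**2. Reproduce the stated operating characteristics.** The rule declares safety if X ≤ 2, with X binomial (n = 20, p):

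P(X ≤ 2) = (1−p)^20 + 20·p·(1−p)^19 + 190·p²·(1−p)^18

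- p = 0.25: 0.0032 + 0.0211 + 0.0669 = 0.0913 (rounded from unrounded terms). Stated type 1 error: 9.1%.
- p = 0.05: 0.3585 + 0.3774 + 0.1887 = 0.9245 (likewise). Stated power: 92.5%.

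Both agree to the stated rounding. The calculation uses only n, the threshold and p. The window decides what p describes but does not enter the formula.

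**3. Size the gap.** The protocol gives no Day -8 death risk, so a risk q is assumed and varied. Let P be the total probability of death from Day -8 to Day +100, held at 0.25 or 0.05. The written rule counts deaths with probability P − q. The chance of declaring safety is then P(X ≤ 2) at n = 20 and p = P − q.

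| Assumed q | Safe, P = 0.25 | Change (points) | Safe, P = 0.05 | Change (points) |
|---|---|---|---|---|
| 0 (all deaths counted) | 9.13% | – | 92.45% | – |
| 0.01% | 9.14% | +0.02 | 92.49% | +0.04 |
| 0.1% | 9.29% | +0.16 | 92.81% | +0.35 |
| 0.5% | 9.96% | +0.83 | 94.14% | +1.69 |
| 1% | 10.85% | +1.73 | 95.61% | +3.16 |

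Changes are taken from unrounded values. The chance of at least one Day -8 death among 20 patients is 1 − (1−q)^20. It is 0.20% at q = 0.01% and 1.98% at q = 0.1%. The last two rows show where the gap would begin to be visible; nothing in the protocol suggests a risk that high after one priming dose.

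**4. Effect of the correction.** With the window opening on Day -8, every death from first dose onward is counted and P covers Day -8 to Day +100. N, the threshold and the 9.1% and 92.5% figures are unchanged.

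**The case against.** The strongest reply is that 13.51 defines transplant-related mortality and never claims to run from the first study dose. Day -7 is when the conditioning backbone begins, and the hypotheses refer to non-relapse mortality with that backbone in a paediatric series, so starting there is defensible. That stands as a possible rationale. The protocol does not give it, however, and the conclusion drawn from the count concerns uproleselan, whose first dose precedes the window.

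A second reply is that a Day -8 death would not go unnoticed. Section 5.2 reports that "Reactions to uproleselan infusions have not been observed to date". Section 7.5 requires notice within 24 hours "of all SAEs that occur after the patient has provided informed consent". Under section 12.2 the DSMC regularly reviews all deaths, and "The DSMC will also meet on an ad hoc basis to review the results of interim analyses or if unexpected safety events occur". This stands in full and is the main reason the point is minor. The DSMC can act on a single death, whereas the 3-of-20 rule only suspends enrolment for its consideration. It does not put the death into the prespecified count.

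Two stronger readings should be resisted. A reader might suppose that a Day -8 death has already occurred and infer that the rule behaves very differently with and without it. That describes a conditional event for which the documents give no rate, not the rule's operating characteristics.

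A reader might also infer that the rule's 20 patients are left open, because section 13.1.1 replaces a Phase 1 patient who dies on Day -8 while 13.1.2 keeps anyone with one dose at the RP2D. But 13.1.1 governs dose determination and 13.1.2 governs efficacy. Section 13.1.3 already includes every eligible patient with at least one dose, in both phases, for reporting toxicities. It does not expressly set the 20 for 13.51, but it is the closest definition, and replacement for dose-finding does not remove a patient from it.

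**Conclusion.** The point holds as a wording mismatch: the mortality window opens one day after uproleselan starts, and a death on Day -8 would fall outside the count behind the safety declaration. It is not an error in the stated power or type 1 error, both of which reproduce.

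The size rests on an assumed Day -8 death risk, since the protocol gives none. At 0.1% or less, the chance of declaring safety shifts by under 0.4 percentage points at either hypothesis. If no patient dies on Day -8, nothing changes. Expedited reporting and DSMC review would cover such a death outside the rule. The documents do not support reading this as a failure of safety oversight. It is a free improvement of the lowest severity.

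**What to change.** In section 13.51, define TRM as death from any cause from the first dose of uproleselan (Day -8) through Day +100. Keep N=20, the threshold of three deaths, the DSMC action and the stated 9.1% and 92.5%.

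Do not add a rule that a replaced Phase 1 patient must hold one of the 20 places. If accrual still continued to 20 evaluable patients, 21 would have been treated at the RP2D and one of them could fall outside TRM monitoring altogether. Leave the 13.52 window alone as part of this change: section 5.3 evaluates regimen-related toxicity only from Day 0 to Day +30, so that window raises a different question.

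The cost is one amended sentence. No new data are needed, because deaths are already reportable as serious adverse events from consent.

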# Table 10. One-stage stopping rule for treatment-related mortality for patients treated at the RP2D

Decision Rule	Action
$\geq$ 3 transplant-related deaths out of 20 patients	Trial termination recommended.
$\leq$ 2 transplant-related deaths out of 20 patients	Uproleselan is safe for further investigation in pediatric patients

This one-stage rule has 92.5% power with an 9.1% type 1 error rate to test the null hypothesis that P>0.25 versus the alternative that P<0.05, where P is the probability of a transplant-related
death. The choice of the null and alternative hypothesis is based on an observed non-relapse mortality of 10.3% at 3 years for the BFC trial of pediatric patients in the Netherlands.

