## 13.52 Monitoring rule for RRT

A one-stage stopping rule will monitor regimen-related toxicity (RRT) for the N=20 patients treated at the RP2D. RRT is defined as the occurrence of dose limiting toxicities as outlined in Table 4, from Day -7 pre-transplant to post-transplant Day +30.

The one-stage interim monitoring rule RRT is presented in Table 11. If there are 3 or more patients with dose limiting RRT in the 20 patients treated at the RP2D, enrollment to the trial will be suspended so that DSMC can consider terminating the trial. If there are 2 or fewer patients with RRT in the 20 patients treated at the RP2D, this is evidence in support of safe use of uproleselan for further investigation in pediatric patients.

The choice of the null and alternative hypothesis is derived from two early phase clinical trials of conditioning with busulfan and a purine analogue. In a trial of fludarabine and busulfan in adolescents and adults transplanted for hematologic malignancies, where busulfan exposure was escalated, 5 of 40 patients (12.5%) receiving busulfan targeted to an average AUC 6, 000  $\mu$ Molmin developed grade 4 regimen related toxicity (based on CTCAE criteria, mucositis and/or transaminitis){Perkins, 2012 #76}. In a phase 1/2 trial in children and adults transplanted for hematologic malignancies, 1 of 22 patients (4.5%) receiving fludarabine 10 mg/m2, clofarabine 30 mg/m2 and busulfan targeted to an average AUC 6, 000  $\mu$ Molmin developed grade 4 regimen related toxicity (based on CTCAE criteria){Andersson, 2011 #59}.

Decision Rule	Action		
≥3 RRTs out of 20 patients	Trial termination recommended.		
≤2 RRT out of 20 patients	Evidence supports safety of uproleselan for		
	further investigation in pediatric patients		

 Table 11. One-stage stopping rule for RRT for patients treated at the RP2D

This one-stage rule has 94% power with an 9.3% type 1 error rate to test the null hypothesis that P>0.185 versus the alternative that P<0.020, where P is the probability of a transplant-related death. The choice of the null and alternative hypothesis is based on sinusoidal obstruction syndrome accounting for the majority of severe RRT in HSCT and an expected incidence of severe VOD of approximately  $10\%^{35}$ 

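### The TRM rule declares uproleselan safe without reference to the RRT rule, so the same 20 patients can yield both a safety declaration and a recommendation to terminate

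*Protocol*

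**What the plan says.** Protocol Section 13.5 contains two numeric rules.

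- **TRM (Section 13.51, Table 10).** "A one-stage stopping rule will monitor transplant-related mortality (TRM) for the N=20 patients treated at the RP2D". The event is broad: "TRM is defined as the occurrence of death from any cause from Day -7 pre-transplant to post-transplant Day +100". With 2 or fewer deaths, "uproleselan will be declared as safe for further investigation in pediatric patients". Table 10 repeats this as a flat statement: "Uproleselan is safe for further investigation in pediatric patients". The note to the table gives the operating characteristics, "This one-stage rule has 92.5% power with an 9.1% type 1 error rate", for the "null hypothesis that P>0.25 versus the alternative that P<0.05".
- **RRT (Section 13.52, Table 11).** "A one-stage stopping rule will monitor regimen-related toxicity (RRT) for the N=20 patients treated at the RP2D". At "3 or more patients with dose limiting RRT in the 20 patients treated at the RP2D", enrollment is suspended so that the DSMC can consider ending the trial, and the action in Table 11 is a recommendation to terminate. Passing this rule is worded more softly than passing the TRM rule: it counts only as supporting evidence of safety.

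No section makes one rule depend on the other or says which prevails. The Phase 2 Design text in Section 5.1, the opening of Section 13 and Section 13.2.4 mention only the TRM rule.

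The phase 2 primary endpoint (Section 13.2.1) is DLT, which Section 5.3 defines as RRT or failure of engraftment. Section 13.52 limits RRT to the organ toxicities of Table 4.

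**The concern.** Take one death and three non-fatal grade 3 hepatic toxicities among the 20. Table 10 says safe for further study; Table 11 recommends termination. Both follow from the rules as written.

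Because passing the TRM rule produces a declaration and passing the RRT rule produces only supporting evidence, mortality alone decides the stated safety conclusion. Yet the primary endpoint is toxicity and engraftment, not death. Section 2.4 presents this study as preparation for a full-scale trial, so the safety sentence is the one that will be carried forward. It is open to contradiction when organ toxicity is high and early deaths are few.

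Non-fatal graft failure enters neither count, although Sections 2.1.2 and 7.1.1 name impaired engraftment as a particular concern with this drug.

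**Working it through.** **1. Reproduce the TRM rule.** With X ~ Binomial(20, p) and a declaration when X ≤ 2:

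- P(X ≤ 2 | p = 0.05) = 0.9245, the stated 92.5%.
- P(X ≤ 2 | p = 0.25) = 0.0913, the stated 9.1%.

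Both agree.

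**2. Reproduce the RRT rule.** With the printed cut-off of 2 or fewer of 20:

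- P(X ≤ 2 | 0.02) = 0.9929, against a stated 94%.
- P(X ≤ 2 | 0.185) = 0.2563, against a stated 9.3%.

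These do not agree. With 1 or fewer of 20 the values are 0.9401 and 0.0926, which do. Steps 3 to 5 use the printed cut-off (stop at 3 or more).

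**3. RRT rates tried.** All appear in Section 13.52:

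- 2%: the rule's alternative
- 4.5%: 1 of 22 in the cited fludarabine, clofarabine and busulfan trial
- 10%: expected severe VOD
- 12.5%: 5 of 40 in the cited fludarabine and busulfan trial
- 18.5%: the rule's null

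They are illustrations. The two trial rates are CTCAE grade 4 rather than Table 4 thresholds, and the 10% is for VOD alone.

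**4. Chance of conflict.** The quantity is P(TRM ≤ 2 and RRT ≥ 3 in the same 20). The protocol does not give the dependence between the two events, so two cases are shown, with t the true TRM and r the true RRT rate.

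- *Independence:* P(TRM ≤ 2) × P(RRT ≥ 3). At t = 5% and r = 10%, 0.9245 × 0.3231 = 0.299.
- *Maximum overlap, r > t:* every death is also an RRT. Then R ~ Binomial(20, r), deaths given R ~ Binomial(R, t/r), and the conflict is the sum over R ≥ 3 of P(R) × P(deaths ≤ 2 | R).
- *Maximum overlap, r ≤ t:* every RRT patient is also a death, so 3 RRTs imply 3 deaths and the conflict is 0.

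With true TRM 5%:

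| True RRT | P(RRT ≥ 3) | Conflict, maximum overlap | Conflict, independence |
|---|---|---|---|
| 2% | 0.007 | 0 | 0.007 |
| 4.5% | 0.059 | 0 | 0.054 |
| 10% | 0.323 | 0.248 | 0.299 |
| 12.5% | 0.465 | 0.389 | 0.430 |
| 18.5% | 0.744 | 0.668 | 0.688 |

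If true TRM is 10.3%, the three-year non-relapse mortality cited under Table 10, the ranges are 0 to 0.21 at RRT 10%, 0.12 to 0.31 at 12.5% and 0.40 to 0.49 at 18.5%.

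**5. Effect of requiring both criteria.** The chance of a declaration falls by exactly the conflict probability. At TRM 5% under independence, P(TRM ≤ 2) × P(RRT ≤ 2) is:

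| True RRT | TRM rule alone | Both rules |
|---|---|---|
| 2% | 0.925 | 0.918 |
| 4.5% | 0.925 | 0.870 |
| 10% | 0.925 | 0.626 |
| 12.5% | 0.925 | 0.495 |
| 18.5% | 0.925 | 0.237 |

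**6. Sensitivity to the RRT cut-off.** If the RRT rule stopped at 2 or more, the conflict under the present wording at TRM 5% and RRT 18.5% would be 0.9245 × (1 − 0.0926) = 0.84 under independence.

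**The case against.** The best defence is that the two rules are sibling parts of one monitoring plan, and either can send the trial to the DSMC. The text of 13.52 asks the DSMC only to consider termination; the recommendation appears only in Table 11. The TRM wording is limited to further investigation. RRT is read at Day +30 and TRM at Day +100, so an RRT signal would normally reach the DSMC before TRM is complete. If the trial closed before 20 patients were treated, the TRM declaration would not be read on 20 at all.

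This softens the conflict but does not remove it. Both rules are written for the full 20. DSMC discretion under one rule does not withdraw the declaration under the other, and even a qualified declaration conflicts with a recommendation to terminate.

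Three stronger readings are tempting, and the protocol does not support them.

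- **That graft failure goes unmonitored.** It is part of DLT and so of the phase 2 primary endpoint. DLTs need expedited reporting (Section 7.5), graft failure and rejection between Day +30 and Day +100 are deemed SAEs (Section 7.3), and the DSMC reviews all adverse events (Section 12.2). Having no numeric boundary for it in a 20-patient single-arm study is a design choice. What stands is narrower: the declaration does not take it into account.
- **That the conflict is likely whatever the truth.** At the rule's own alternative of 2%, and at the 4.5% seen with the same conditioning drugs, it is uncommon.
- **That requiring both criteria costs almost nothing in the chance of a declaration.** That holds only near an RRT rate of 2%.

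**Conclusion.** The point holds as a defect in how the safety conclusion is worded. Followed exactly, Section 13.51 with Table 10 and Section 13.52 with Table 11 can give incompatible conclusions on the same 20 patients, and nothing in the protocol resolves them.

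The size depends on the true RRT rate. At TRM 5% the conflict is at most about 5% for RRT rates of 4.5% or below, about one in four or more at 10%, and about two in three at the 18.5% the protocol treats as unacceptable. It is therefore most frequent when toxicity is worst.

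These figures assume that all 20 patients are assessed for both endpoints, that deaths and RRT are either independent or overlap positively, and that the printed RRT cut-off of 3 or more stands. That cut-off is itself in doubt, because its stated operating characteristics belong to a different threshold.

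The reverse conflict (3 or more deaths, 2 or fewer RRTs) is milder, since passing the RRT rule claims only supporting evidence.

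**What to change.** 1. **Reconcile the RRT rule first.** The printed cut-off (2 or fewer of 20 passes; exact 99.3% power and 25.6% type 1 error) and the stated 94% and 9.3% (which match 1 or fewer of 20) cannot both stand. The sponsor must settle which was intended before a joint declaration is built on it.
2. **Reword Section 13.51 and Table 10** so that 2 or fewer deaths means only that the TRM criterion is met.
3. **State the safety declaration once, in Section 13.5**, to be made only when the TRM and RRT criteria are both met. Align the Table 11 wording with this.
4. **Report the number of engraftment failures among the 20 alongside the declaration.** Section 12.2 ends DSMC outcome review once product administration has finished for all subjects, so this count should be part of the reported result rather than left to DSMC review.

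The cost is wording only: no added patients, visits or data. The chance of a declaration falls as shown in step 5 of the working. The loss is negligible at RRT 2% (0.925 to 0.918), material at 10% (to 0.63) and large at 18.5% (to 0.24). The last is the intended effect when toxicity is high. The sponsor should see these figures before adopting the change, and they must be recalculated if step 1 alters the RRT cut-off.
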